9.8.2. Serious Adverse Events

An SAE is any untoward medical occurrence that at any dose:

- Results in death
- Is life-threatening*
- Requires inpatient hospitalization or prolongation of existing hospitalization
- Congenital anomaly/birth defect

- Persistent or significant incapacity or substantial disruption of the ability to conduct normal life functions

**Life-threatening AE. An AE is considered “life-threatening” if, in the view of either the Investigator or Sponsor, its occurrence places the patient or subject at immediate risk of death. It does not include an AE that, had it occurred in a more severe form, might have caused death.*

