9.9. Methods and Timing for Assessing, Recording, and Analyzing Safety Parameters

9.9.1. Adverse Events

AEs will be collected at Day 1 during and after dosing. Any medical condition that is present at the time that the subject is screened should be considered as baseline and not reported as an AE. However, if the condition increases in severity or frequency at any time during the study, it should be recorded as an AE.

All AEs must be graded for severity and relationship to study product based on the Investigator’s assessment.

The Investigator will assess the intensity of AEs based on the following definitions per Toxicity Table (modified from FDA Toxicity Grading Scale for Healthy Adult and Adolescent Volunteers Enrolled in Preventive Vaccine Clinical Trials):

- Mild: Grade 1 (awareness of sign or symptom, but easily tolerated)
- Moderate: Grade 2 (discomfort sufficient to cause interference with normal activities)
- Severe: Grade 3 (incapacitating, with inability to perform normal activities)
- Potentially Life Threatening: (Grade 4)

- Death: (Grade 5)

It is important to distinguish between serious and severe AEs. Severity is a measure of intensity whereas seriousness is defined by the criteria in [Section 9.8.2](#).

An AE of severe intensity need not necessarily be considered serious. For example, nausea that persists for several hours may be considered severe nausea, but not an SAE. On the other hand, a stroke that results in only a limited degree of disability may be considered a mild stroke but would be an SAE.

For an AE to be a suspected drug-related event, there should be at least a reasonable possibility of a causal relationship between the study drug and the AE.

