9.10.2. Serious Adverse Events

The following procedures will apply to all SAEs:

- The PI will report any SAE to ICON Pharmacovigilance Safety System (PVSS) within 24 hours of awareness.
- ICON PVSS will perform an initial check of the SAE and contact the site for any missing elements and then inform the ICON MM of the SAE.
- ICON PVSS will record the information on the appropriate SAE report form and send to RGS.
- Each SAE will be reviewed and followed to resolution or stability by a study physician.
- SAEs will be collected on each subject up to 60 days after his/her last study visit.

Any AE that meets a protocol-defined serious criterion must be submitted immediately (within 24 hours of site awareness) on an SAE form to ICON PVSS, at the following address and ICON PVSS will send AE/SAE information to Resilience Government Services, Inc.

ICON PVSS	ICON plc PVSS [REDACTED] [REDACTED] [REDACTED]
ICON Medical Monitor	[REDACTED]
ICON PVSS will send AE/SAE information to Resilience Government Services, Inc.	
Resilience Government Services	Resilience Government Services, Inc. [name] SAE Fax Number: [REDACTED] SAE Email Address: [REDACTED]

Other supporting documentation of the event may be requested by ICON PVSS and should be provided as soon as possible.

ICON plc PVSS will send SAEs with the ICON Drug Safety Physician assessment of causality, expectedness, and any impact on the benefit-risk ratio of the IP to RGS. The DOD and the FDA will be notified of SAEs as appropriate, by RGS. HRPO and IRB will be informed of any safety issues as appropriate, per safety management plan by ICON and the PI.

If the Investigator becomes aware of an SAE that is suspected to be related to study product up to 60 days after the subject completes the study, the Investigator will report the event to ICON PVSS.

If a non-serious AE becomes serious, this and other relevant follow-up information must also be provided to ICON within one day as described above. For a non-serious AE that becomes serious, but which is not fatal or life-threatening, a report should be received within 5 days.

All SAEs have to be reported, whether or not considered causally related to the IP or to the study procedure(s). All SAEs will be recorded in the CRF. The Investigator is responsible for informing the IEC of the SAE as per local requirements. The Investigator should report to ICON, who will forward the report to the appropriate Sponsor representative.

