Pregnancy

Pregnancies that occur during the study period will be reported to ICON PVSS on the Pregnancy Report form within 5 days of site awareness.

Efforts will be made to follow all pregnancies occurring prior to 56 days post product administration through to outcome, as described in the Safety Management Plan (e.g., delivery, spontaneous abortion or therapeutic abortion).

Pregnancy itself is not regarded as an AE unless there is a suspicion that the study drug may have interfered with the effectiveness of a contraceptive medication. However, the outcome of all pregnancies (spontaneous miscarriage, elective termination, normal birth or congenital abnormality) must be followed up and documented even after the patient has been withdrawn from the study.

Male subjects participating in this study should report pregnancies of their partners and outcome of the pregnancy, if fathered during the conduct of the study.

All reports of congenital abnormalities/birth defects are SAEs. Spontaneous miscarriages should also be reported and handled as SAEs. Elective abortions without complications should not be handled as AEs. All outcomes of pregnancy must be reported to the Sponsor on a pregnancy outcomes report form.

A positive urine pregnancy test for a female subject will result in subject discontinuation from the study. Such subject will have follow-ups for pregnancy outcomes. The outcome of pregnancy will be documented even after completion of the study.

All reports of congenital abnormalities/birth defects/preterm (< 37 weeks gestation) are SAEs. Spontaneous miscarriages should also be reported and handled as SAEs. Elective abortions without complications should not be handled as SAEs but should be reported as a follow-up report for outcome of the pregnancy. All outcomes of pregnancy must be reported to ICON on a Pregnancy Outcomes Report Form.

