9.12. Halting Rules

9.12.1. Halting Criteria for the Study

Study dosing may be halted after review of data by the MM in consultation with RGS ML. The Data Safety Monitoring Board (DSMB) will be informed and a review of available safety data will be conducted by the DSMB if any of the following occur:

- Death of a subject following injection and prior to the subject's last visit that was possibly related to study product
- Two Grade 4 non-laboratory AE (as per FDA guidance toxicity table as modified in [Appendix B](#)) related to study treatment, or

- One life-threatening allergic/hypersensitivity reaction (anaphylaxis) in any subject, manifested by bronchospasm with or without urticaria or angioedema, or
- Requiring hemodynamic support with pressor medications or mechanical ventilation, or
- One SAE that is considered definitely or possibly related to study product
- Four or more subjects with a Grade 3 AE in the same organ class (systemic toxicity, clinical laboratory tests or vital signs) possibly related to study drug

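### The SAE definition has no medical-judgement criterion, so a related hypersensitivity reaction treated without admission, not judged life-threatening and without incapacity is classed as non-serious

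*Protocol*

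**What the plan says.** Protocol 9.8.2 lists five criteria. The three that matter here are death ("Results in death"), life-threatening, and admission ("Requires inpatient hospitalization or prolongation of existing hospitalization"); the others are congenital anomaly and incapacity. Life-threatening means that, "in the view of either the Investigator or Sponsor, its occurrence places the patient or subject at immediate risk of death". A limit follows: "It does not include an AE that, had it occurred in a more severe form, might have caused death".

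Other sections depend on this list:

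- Protocol 9.9.1 refers seriousness back to 9.8.2.
- Protocol 9.10.2 sets the fast report: "Any AE that meets a protocol-defined serious criterion must be submitted immediately (within 24 hours of site awareness".
- Protocol 9.10.2, under Pregnancy, adds categories that 9.8.2 does not name. One is miscarriage ("Spontaneous miscarriages should also be reported and handled as SAEs"); preterm birth is the other.
- Protocol 9.12.1 lists what sends the data to the DSMB. One bullet is "One SAE that is considered definitely or possibly related to study product". Separate bullets cover one life-threatening anaphylactic reaction with bronchospasm, and pressor or ventilator support. Two related Grade 4 non-laboratory AEs, or four subjects with a possibly related Grade 3 AE in one organ class, also qualify.
- SAP 9.10.1 tabulates SAEs and related SAEs as part of primary endpoint 1a, alongside all AEs, medically attended AEs, Grade 3 or higher AEs and related AEs.

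**The concern.** Every criterion in 9.8.2 is an outcome. None lets the Investigator or Sponsor call an event serious because it was medically important, or because treatment prevented one of the listed outcomes.

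The gap falls on a risk the protocol names itself. Section 3.3.1 lists bronchospasm and angioedema among the reactions seen with monoclonal antibodies, and 9.7 requires epinephrine, corticosteroids and bronchodilators at every site. A reaction that is treated promptly and sent home is a foreseeable event in this trial.

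Three things are at stake for such an event: how fast the sponsor hears of it, whether it is counted in the SAE part of a primary endpoint, and whether a single case prompts DSMB review as a related SAE.

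**Working it through.** The plan gives no figure to reproduce; Protocol 11.1 states that there is no formal sample size calculation. The check traces one event through the documents, then illustrates what the event counts mean.

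**Step 1. The event.** A related bronchospasm, angioedema or generalised urticaria, treated on site or in an emergency room and not admitted.

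**Step 2. Two branches under 9.8.2.**

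| | (a) Judged an immediate risk of death | (b) Not so judged, no incapacity |
|---|---|---|
| Serious under 9.8.2 | Yes, wherever treated | No |
| 24-hour SAE form (9.10.2) | Yes | No |
| SAE rows (SAP 9.10.1) | Yes | No |
| Related-SAE bullet (9.12.1) | Yes | No |
| Other single-event bullets (9.12.1) | Anaphylaxis bullet if bronchospasm is present | Only if the pressor or ventilator bullet applies |
| All-AE and related-AE tables | Yes | Yes |
| Medically attended and Grade 3+ rows | If it qualifies | If it qualifies |

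The gap is branch (b) without pressor or ventilator support. Hypotension is left out of the examples because the pressor bullet may apply to it.

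**Step 3. What catches branch (b).**

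- Medically attended AEs (9.8.4) turn on an unscheduled healthcare visit. A reaction treated during the planned 1-hour or 8-hour stay may not qualify. These events go on the CRF under 9.10.1, without a 24-hour report.
- Appendix B has no row for bronchospasm, angioedema, urticaria or hypersensitivity. Grading falls to the general scale in 9.9.1, so Grade 3 or Grade 4 depends on judgement. Review then needs two Grade 4 events or four subjects with Grade 3.
- SAP 4.2 plans one DSMB meeting for Cohort 4.

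**Step 4. Illustration for branch (b) only.** Inputs: n = 200 active subjects in Cohort 4 (SAP 3.1), and an assumed rate p per subject, which the documents do not give. Subjects are taken as independent, with at most one event each.

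P(X ≥ r) = 1 − Σ C(200, k) pᵏ (1 − p)²⁰⁰⁻ᵏ, summed over k = 0 to r − 1.

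For p = 0.5%: P(X ≥ 1) = 1 − 0.995²⁰⁰ = 1 − 0.367 = 0.633. Then P(X ≥ 2) = 0.633 − 200 × 0.005 × 0.995¹⁹⁹ = 0.633 − 0.369 = 0.264.

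| Assumed p | 1 or more | 2 or more | 4 or more |
|---|---|---|---|
| 0.25% | 39.4% | 9.0% | 0.2% |
| 0.5% | 63.3% | 26.4% | 1.9% |
| 1% | 86.6% | 59.5% | 14.2% |

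The first column is the chance of meeting the related-SAE bullet if these events counted as SAEs. The second applies if all were Grade 4. The third applies if all were Grade 3, and is an upper limit because that bullet also requires the same organ class.

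**The case against.** A reader might infer that any related hypersensitivity reaction treated without admission is non-serious and can prompt no single-event review. The documents do not support that. Life-threatening does not depend on the place of care, and the view of either the Investigator or the Sponsor is enough. Section 9.12.1 also has its own anaphylaxis and pressor or ventilator bullets.

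Nor is the 9.12.1 list the only route to action. The medical monitor and the sponsor's medical lead can each recommend convening the DSMB over any safety concern (9.13.1, 9.13.2), and the DSMB receives AE and medically attended AE incidences and listings (SAP 4.2). Branch (b) events are not lost from the analysis.

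Some internal evidence is weaker than it looks. Section 9.9.1 says "a stroke that results in only a limited degree of disability may be considered a mild stroke but would be an SAE", which might be read as proof that the list is too short. It illustrates severity against seriousness, and a stroke could meet the admission or incapacity criterion. Appendix B makes an emergency-room visit Grade 4 in several rows, such as headache and myalgia, but none is a hypersensitivity row, and 9.9.1 separates severity from seriousness on purpose. The pregnancy text shows that the authors needed SAE categories beyond the list; it says nothing about hypersensitivity.

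All of this stands and limits the point. It does not supply the missing criterion. Convening the DSMB is discretionary, and no other rule gives a branch (b) event a 24-hour report.

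**Conclusion.** The point holds for a defined subset: related reactions that are not admitted, not judged an immediate risk of death, cause no incapacity and need no pressor or ventilator support. For these the plan states a rule that makes them non-serious, so this is more than a missing detail. What is lost is SAE classification, speed of reporting and the single-event related-SAE bullet. The AE record itself is kept. The SAE count could be lower than the clinical picture for this subset; the documents do not show that it will be.

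The probabilities rest on assumed rates and describe only this subset, not emergency-room-treated reactions in general. Protocol 3.1.3 says that Cohorts 1-3 have completed their last visits, so the effect is mainly on Cohort 4. The protocol supplied is dated 12 Apr 2024, while the SAP refers to version 5.0 of 06-JAN-2025, so 9.8.2 should be checked in that version. The point should be addressed; it does not put the trial's main conclusions in doubt.

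**What to change.** Add one reporting criterion to 9.8.2: an important medical event that, in the Investigator's or Sponsor's judgement, may jeopardise the subject or require intervention to prevent one of the listed outcomes. Use that definition for SAE reporting and for the SAE tables in SAP 9.10.1.

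Reconcile 9.8.2 with the pregnancy text in 9.10.2, the bullets in 9.12.1 and the Grade 4 wording in Appendix B. A wider SAE definition would feed into the related-SAE bullet, so the sponsor should state how the two relate. No halting rule is proposed here.

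If Cohort 4 dosing is already complete, a documented blinded review of non-serious reactions against the new criterion before database lock would still improve the SAE rows.

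The cost is one bullet, matching guidance on the SAE form and a slightly higher SAE count. If only Cohort 4 uses the new definition, any SAE row set beside Cohorts 1-3 mixes two definitions and needs a footnote.

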9.8.3. Unexpected

An adverse reaction, the nature or severity of which is not consistent with the applicable product information (e.g., Investigator’s Brochure [IB] for an unapproved IP or package insert/summary of product characteristics for an approved product).

9.8.4. Medically-Attended Adverse Event

A medically-attended AE is any AE or SAE that leads to an unscheduled visit to a healthcare practitioner. A medically-attended AE may include but is not limited to:

- Local (injection site) or systemic symptoms, PE findings, laboratory abnormalities, new clinical conditions or syndromes, or worsening of pre-existing conditions, in study subjects that result in an encounter with a medical professional in either an outpatient or inpatient setting, at any time from receipt of study drug/placebo through the end of the study.

Medically-attended AEs must be documented and graded according to the toxicity grading scale in [Appendix B](#).

9.9. Methods and Timing for Assessing, Recording, and Analyzing Safety Parameters

9.9.1. Adverse Events

AEs will be collected at Day 1 during and after dosing. Any medical condition that is present at the time that the subject is screened should be considered as baseline and not reported as an AE. However, if the condition increases in severity or frequency at any time during the study, it should be recorded as an AE.

All AEs must be graded for severity and relationship to study product based on the Investigator’s assessment.

The Investigator will assess the intensity of AEs based on the following definitions per Toxicity Table (modified from FDA Toxicity Grading Scale for Healthy Adult and Adolescent Volunteers Enrolled in Preventive Vaccine Clinical Trials):

- Mild: Grade 1 (awareness of sign or symptom, but easily tolerated)
- Moderate: Grade 2 (discomfort sufficient to cause interference with normal activities)
- Severe: Grade 3 (incapacitating, with inability to perform normal activities)
- Potentially Life Threatening: (Grade 4)

- Death: (Grade 5)

It is important to distinguish between serious and severe AEs. Severity is a measure of intensity whereas seriousness is defined by the criteria in [Section 9.8.2](#).

An AE of severe intensity need not necessarily be considered serious. For example, nausea that persists for several hours may be considered severe nausea, but not an SAE. On the other hand, a stroke that results in only a limited degree of disability may be considered a mild stroke but would be an SAE.

For an AE to be a suspected drug-related event, there should be at least a reasonable possibility of a causal relationship between the study drug and the AE.

9.9.2. Relationship to Study Product

AEs and SAEs must be assessed by the Investigator to determine relationship to study product. All AEs must have their relationship to study product assessed using the following terms:

- **Definitely Related:** There is a definite probability that the study product caused the AE.
- **Possibly Related:** There is a reasonable possibility that the study product caused the AE. Reasonable possibility means that there is evidence to suggest a causal relationship between the study product and the AE.
- **Not Related:** There is not a reasonable possibility that the administration of the study product caused the event.

To help assess, the following factors may be considered:

- Temporal relationship of the event to the administration of study product
- Whether an alternative etiology has been identified
- Biological plausibility
- Existing therapy and/or concomitant medications

9.10. Reporting Procedures

9.10.1. Adverse Events

AEs to include medically-attended AEs not meeting the criteria for “SAEs” will be captured on the appropriate Case Report Form (CRF). Information to be collected for AEs includes event description, date of onset, investigator assessment of severity, relationship to study product, date of resolution of the event, seriousness, and outcome.

The following variables will be recorded for each AE: verbatim/AE description, time and date for AE start and stop, maximum intensity, seriousness, causality rating, whether or not the AE caused the patient to discontinue, and the outcome.

9.10.2. Serious Adverse Events

The following procedures will apply to all SAEs:

- The PI will report any SAE to ICON Pharmacovigilance Safety System (PVSS) within 24 hours of awareness.
- ICON PVSS will perform an initial check of the SAE and contact the site for any missing elements and then inform the ICON MM of the SAE.
- ICON PVSS will record the information on the appropriate SAE report form and send to RGS.
- Each SAE will be reviewed and followed to resolution or stability by a study physician.
- SAEs will be collected on each subject up to 60 days after his/her last study visit.

Any AE that meets a protocol-defined serious criterion must be submitted immediately (within 24 hours of site awareness) on an SAE form to ICON PVSS, at the following address and ICON PVSS will send AE/SAE information to Resilience Government Services, Inc.

ICON PVSS	ICON plc PVSS [REDACTED] [REDACTED] [REDACTED]
ICON Medical Monitor	[REDACTED]
ICON PVSS will send AE/SAE information to Resilience Government Services, Inc.	
Resilience Government Services	Resilience Government Services, Inc. [name] SAE Fax Number: [REDACTED] SAE Email Address: [REDACTED]

Other supporting documentation of the event may be requested by ICON PVSS and should be provided as soon as possible.

ICON plc PVSS will send SAEs with the ICON Drug Safety Physician assessment of causality, expectedness, and any impact on the benefit-risk ratio of the IP to RGS. The DOD and the FDA will be notified of SAEs as appropriate, by RGS. HRPO and IRB will be informed of any safety issues as appropriate, per safety management plan by ICON and the PI.

If the Investigator becomes aware of an SAE that is suspected to be related to study product up to 60 days after the subject completes the study, the Investigator will report the event to ICON PVSS.

If a non-serious AE becomes serious, this and other relevant follow-up information must also be provided to ICON within one day as described above. For a non-serious AE that becomes serious, but which is not fatal or life-threatening, a report should be received within 5 days.

All SAEs have to be reported, whether or not considered causally related to the IP or to the study procedure(s). All SAEs will be recorded in the CRF. The Investigator is responsible for informing the IEC of the SAE as per local requirements. The Investigator should report to ICON, who will forward the report to the appropriate Sponsor representative.

Pregnancy

Pregnancies that occur during the study period will be reported to ICON PVSS on the Pregnancy Report form within 5 days of site awareness.

Efforts will be made to follow all pregnancies occurring prior to 56 days post product administration through to outcome, as described in the Safety Management Plan (e.g., delivery, spontaneous abortion or therapeutic abortion).

Pregnancy itself is not regarded as an AE unless there is a suspicion that the study drug may have interfered with the effectiveness of a contraceptive medication. However, the outcome of all pregnancies (spontaneous miscarriage, elective termination, normal birth or congenital abnormality) must be followed up and documented even after the patient has been withdrawn from the study.

Male subjects participating in this study should report pregnancies of their partners and outcome of the pregnancy, if fathered during the conduct of the study.

All reports of congenital abnormalities/birth defects are SAEs. Spontaneous miscarriages should also be reported and handled as SAEs. Elective abortions without complications should not be handled as AEs. All outcomes of pregnancy must be reported to the Sponsor on a pregnancy outcomes report form.

A positive urine pregnancy test for a female subject will result in subject discontinuation from the study. Such subject will have follow-ups for pregnancy outcomes. The outcome of pregnancy will be documented even after completion of the study.

All reports of congenital abnormalities/birth defects/preterm (< 37 weeks gestation) are SAEs. Spontaneous miscarriages should also be reported and handled as SAEs. Elective abortions without complications should not be handled as SAEs but should be reported as a follow-up report for outcome of the pregnancy. All outcomes of pregnancy must be reported to ICON on a Pregnancy Outcomes Report Form.

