9.7. Assessment of Safety

Regulatory requirements including the FDA regulations and International Conference on Harmonization (ICH) Guidelines for GCP set forth safety monitoring and reporting responsibilities of sponsors and investigators to ensure the safety and protection of human subjects participating in clinical trials.

Responsibilities

Investigators participating in this clinical trial are responsible for and will:

- evaluate subject safety including assessment of AEs for seriousness, severity, and causality;
- notify the Sponsor (RGS) of SAEs immediately;
- provide detailed written reports, including necessary documentation requested by the Sponsor or IRB promptly following immediate initial reports;
- inform the IRB of AEs as required by applicable regulatory requirements, and;
- have emergency staff and medications, such as epinephrine, corticosteroids, bronchodilators, and emergency tool kits for emergent intubation and initial acute cardiopulmonary resuscitative care available at all clinical sites in the event they are needed during and immediately after IM injections.

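### Protocol 9.10.2 gives two incompatible limits, one day and 5 days, for reporting a non-fatal, non-life-threatening AE that becomes serious

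*Protocol*

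**What the plan says.** Protocol Section 9.10.2 opens with procedures for all SAEs, the first of which is "The PI will report any SAE to ICON Pharmacovigilance Safety System (PVSS) within 24 hours of awareness". After that list, it says that any AE meeting a serious criterion "must be submitted immediately (within 24 hours of site awareness) on an SAE form to ICON PVSS". Further down it deals with events that change status: "If a non-serious AE becomes serious, this and other relevant follow-up information must also be provided to ICON within one day as described above". The sentence directly after that reads: "For a non-serious AE that becomes serious, but which is not fatal or life-threatening, a report should be received within 5 days".

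Two other places bear on this. Section 9.7 lists among the investigator's duties to "notify the Sponsor (RGS) of SAEs immediately", with no exception. The Pregnancy text within Section 9.10.2 also uses a 5-day limit, but there it states the recipient, the form and that the clock runs from site awareness.

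**The concern.** The last two sentences have the same trigger, a non-serious AE that becomes serious, and give different limits. The second covers a subset of the first and allows longer, so a site could read it as a relaxation for less urgent events. Nothing says whether it is an exception, a limit for a later report, or a leftover.

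What is at stake is the timing of safety review. The formal route to the medical monitor runs through the pharmacovigilance group, which is to "contact the site for any missing elements and then inform the ICON MM of the SAE". Under Section 9.12.1, a single SAE judged definitely or possibly related to study product is enough for the DSMB to be informed and to review the safety data. A late form could hold up that route while Cohort 4 is being dosed (200 subjects planned on active product, SAP Table 1). The ambiguity also makes it unclear whether a report on day 4 is a protocol deviation.

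**Working it through.** No design calculation is involved. The check sets the statements side by side for one event: a non-serious AE that worsens and leads to hospitalization.

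| Source | Trigger | Force | Limit | Recipient | Clock start |
|---|---|---|---|---|---|
| 9.10.2, opening list | any SAE | will | 24 hours | pharmacovigilance group | awareness |
| 9.10.2, paragraph after the list | any AE meeting a serious criterion | must | 24 hours, on an SAE form | pharmacovigilance group | site awareness |
| 9.10.2, change of status | non-serious AE becomes serious | must | one day | ICON | refers back to the text above |
| 9.10.2, next sentence | same, if not fatal or life-threatening | should | 5 days | not stated | not stated |
| 9.7 | SAEs | duty of the investigator | immediately | sponsor | not stated |

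**Do all rows cover the event?** Yes. Once the subject is hospitalized the event is an SAE, meets a serious criterion and has changed status, so the first three rows apply. It is neither fatal nor life-threatening, so the fourth applies too. A report on day 5 would meet the fourth row and fail the first three.

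**Which serious events are exposed?** Section 9.8.2 lists 5 criteria. The 5-day sentence itself excludes death and life-threatening events: 5 − 2 = 3. The Pregnancy text makes every report of a congenital anomaly an SAE, so such an event would not start as a non-serious AE: 3 − 1 = 2. The two left are "Requires inpatient hospitalization or prolongation of existing hospitalization" and "Persistent or significant incapacity or substantial disruption of the ability to conduct normal life functions".

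**How long could the delay be?** Assume the 5-day limit concerns the site's report to the pharmacovigilance group and that both limits run from site awareness in calendar days. The sentence states none of this.

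- Exception reading: 5 − 1 = 4 days.
- Follow-up-report reading: the initial form is still due within one day, so 0 days.

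The documents give no dosing rate, so the number of subjects exposed to such a delay cannot be computed.

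**The case against.** The strongest reply is that this is loose wording with one dominant reading. The 5-day sentence says should, where the others say will or must, and it is not phrased as an exception. A site that reports within 24 hours satisfies every statement. That is true, and it is why the 24-hour rule is the better reading. It does not remove the conflict over the latest permitted time.

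A second reply is that the 5 days belong to a later report. Section 9.7 does separate immediate notice from detailed written reports that follow promptly, and Section 9.10.2 lets the pharmacovigilance group ask for supporting documents afterwards. This is the best textual support for a benign reading. But Section 9.7 gives no number of days, and the one-day sentence in 9.10.2 already takes in relevant follow-up information. A general follow-up limit would also have no evident reason to apply only to events that become serious without being fatal or life-threatening.

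A third is that the 5 days might govern the onward step from the pharmacovigilance group to the sponsor, which has no stated deadline. The sentence names neither sender nor recipient, so this cannot be excluded, but nothing in the text ties it to that step.

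The points about consequence largely stand. The medical monitor is the site's primary contact for safety questions (Section 9.13.1) and may hear of the event directly. Halting is discretionary, Section 9.12.1 sets no time limit for the review, and only product-related SAEs meet that criterion. Cohorts 1-3 had already completed their visits (Section 3.1.3). The supplied protocol is dated 12 Apr 2024, whereas the SAP is written against version 5.0 of 06-JAN-2025, so the sentence may no longer be in force.

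**Conclusion.** The concern holds as a minor error in the supplied protocol. Three mandatory statements give 24 hours or one day, and the adjoining sentence gives 5 days for a subset of the same events. The effect ranges from 0 days to at most 4 days' delay in the formal SAE report, under the assumptions on recipient, clock start and calendar days set out above. It realistically concerns events that become serious through hospitalization or incapacity. Fatal and life-threatening events, the safety endpoint counts and the analyses are unaffected. Version 5.0 was not available, so whether the sentence survives, and whether Cohort 4 dosing continues, could not be checked.

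**What to change.** Check version 5.0 of the protocol first. If the sentence is still there, delete it. Alternatively, replace it with a statement that for every AE that becomes serious the initial SAE form is due to the pharmacovigilance group within 24 hours of site awareness, and that 5 days applies only to a complete follow-up report.

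The cost is one sentence in a protocol amendment, with the IRB approval that Section 13.2 requires, plus a short note to sites if Cohort 4 is still active. Data collection and analysis do not change.
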